7.2.2 Reference arm

Arm 3: Sodium Stibogluconate 20 mg/kg/day Intravenous/Intramuscular (IV/IM) q.d. and Paromomycin 15 mg/kg/day IM q.d. for 17 days

SSG will be given IM/IV at a dose of 20 mg/kg once daily for 17 days. PM base will be administered IM at a dose of 15 mg/kg once daily for 17 days. The dosing regimen will be the combination of both SSG and PM as described above.

7.3. Study treatments labelling, packaging

Commercially available MF, PM and SSG will be used. Trial specific labels will be applied on the boxes prior to use with the following statement "For Clinical Trial use Only" and will include protocol code, Sponsor and PI contact details as well as direction for use.

7.4. Accountability

Study medications must be kept in a locked room that can be accessed only by the pharmacist or designated personnel by the investigator. The study medications must not be used for other purposes other than this protocol. Under no circumstances the investigator or site staff may supply study medications to other investigators or sites, or allow the medications to be used other than as directed by this protocol without prior authorization from DNDi. Under no circumstances can the study specific products (appropriately labelled) be replaced by other commercially available product (not specifically trial labelled).

Specific study forms for drug accountability will be designed to allow for adequate records on receipt, use, return, loss, or other disposition of medications. These accountability forms must be maintained by the study pharmacist or designated personnel and stored in the locked room with the study medication.

7.5. Storage

Study drugs must be kept in a locked cabinet and/or in a room with restricted access, under the control of the study pharmacist.

Temperature of the storage location will be monitored daily and recorded in a temperature log. In the event of temperature excursions below or above the allowable range, site staff will inform the study monitor.

Miltefosine: MF must be stored at 20-25°C; excursions permitted between 15-30°C. The product should be stored in the original package and protected from moisture. The shelf life is 5 years. Packaging should be undamaged prior to use.

Confidential Page 37 of 68

Paromomycin: The product should be stored below 30°C and protected from light. Partially used ampoules must not be stored for future patient use. The shelf life is approximately 3 years. Packaging should be undamaged prior to use.

Sodium Stibogluconate: The product should be stored below 30°C and protected from light. The shelf life is 3 years. The contents should not be used for more than one month after opening.

7.6. Blinding and procedures for unblinding

This is an un-blinded open label study.

7.7. Concomitant treatments

All medications required for concomitant conditions should be postponed until after the end of treatment for VL, unless warranted by immediate medical need. Common conditions such as malaria and respiratory tract infections should be treated prior to starting VL treatment.

Details of all concomitant medications used during the study will be recorded in the patients' charts and in the CRF, with reason for use and dates of administration. Concomitant medications will be coded using the WHO Drug Dictionary Enhanced.

Drugs that prolong the QT interval (e.g. quinine) should be avoided while SSG is being administered. If it is urgently required to give such drugs, SSG should be stopped; otherwise alternatives should be sought (e.g. artemisinin derivatives). For MF, there are no known interactions with other commonly used medications, though this cannot be excluded. While giving PM, the use of other aminoglycosides must be avoided (e.g. gentamicin).

7.8. Rescue treatment

In case of treatment failure or intolerability (treatment must be permanently interrupted), rescue treatment will be provided to the patient, at the discretion of the study physician and based on the national VL treatment guidelines. For patients in arm 1 and 2, rescue treatment is expected to be SSG/PM (SSG 20 mg/kg/day, PM 15 mg/kg/day) or AmBisome multiple dose (30 mg/kg total dose). In arm 3, rescue treatment is expected to be AmBisome multiple dose (30 mg/kg total dose).

Patients will be given rescue treatment if they have:

- failed to respond to MF/PM treatment or to SSG/PM reference treatment within the treatment period (lack of improvement or worsening of the clinical signs and symptoms of VL).
- failed to respond to MF/PM treatment or to SSG/PM reference treatment at the EOT assessments (D28). This will be reflected by positive parasitological assessment and/or lack of improvement or worsening of the clinical signs and symptoms of VL.
- failed to tolerate trial medication / occurrence of adverse event(s) during receipt of trial drugs that requires permanent treatment interruption, and rescue treatment is indicated by the investigator (see section 9).
- relapsed, i.e. recurrence of symptoms, signs and presence of parasites after EOT

Confidential Page 38 of 68

(D28) during the follow up period

• developed severe post kala azar dermal leishmaniasis (PKDL) that necessitates rescue treatment (see section 8.3.4).

8. Study Assessments

8.1. Timing of Assessments

Assessments will be carried out at Screening period (day -7 to 0) and on days 1, 3, 7, 14, 21, 28, 56 and 210. It will include clinical, parasitological, haematological, biochemistry, safety, pharmacokinetic and pharmacodynamics assessments.

A table with the schedule of events is listed under section 5.

All patients will be hospitalized for screening/baseline procedures until completion of day 14 (arm 1 and 2) and day 17 (arm 3) procedures (approximately 21-24 days). Day 28, 56 and 210 assessments will be conducted as outpatient visits.

Assessments performed during study visit at D28 will have allowable window of +1day, due to critical PK assessments at this EOT visit. Therefore, it is acceptable to have patients readmitted at the hospital the day before (D27). In the case of patients coming from very remotes areas, mobilization will be strengthened and it will be allowed to readmit those patients 2 to 3 days before D28 assessments.

All other assessments performed during treatment period (D1 until < D28) will have an allowable window of \pm 1 day. In the follow-up period, visit windows will be: day 56 (\pm 7 days) and day 210 (\pm 14 days).

8.2. Baseline Assessments

The following baseline assessments will be done during screening (and after obtaining patient consent) in order to confirm VL diagnosis and verify inclusion and exclusion criteria.

- Demographic data including age and sex
- Medical history including relevant past history, previous VL episode, concomitant medications and medication taken in previous 14 days
- Clinical examination: Physical examination including clinical signs and symptoms of VL, PKDL assessment, body weight, height, vital signs (Temperature, Heart rate and Blood pressure), spleen and liver size
- Nutritional status: severe malnutrition will be defined as follows*:
- for children aged <5 years with weight-for-height WHO reference curves by sex, z score <-3;
- for patients 5-18 years with BMI-for-age WHO reference curves for sex, z score <
 -3:
- for adults ≥19 years as BMI < 16
- ECG
- Audiometric test
- Clinical safety laboratory evaluations:

Confidential Page 39 of 68

- Haematology: Haemoglobin, total WBC with differential, platelets
- Biochemistry: Alanine aminotransferase (ALT), Aspartate aminotransferase (AST), total bilirubin (TBIL), Creatinine (CRE), Albumin (ALB)
- Urine pregnancy test
- HIV test routine counselling for HIV test will be given for patients' parents, as part of the study informed consent procedure interview or a separate consent will be requested, according to the local requirements. Testing will be done according to national guidelines and undergo a single rapid diagnostic test for the purposes of the clinical trial. If the RDT for HIV is positive, the patient must be excluded from participating in the clinical trial and receive current standard treatment for VL and further assessment and treatment for HIV according to the national HIV treatment Guidelines.
- Spleen, bone marrow or lymph node aspirate for parasitology (microscopy and culture, see additional information in section 8.3.2. Parasitological assessment) and pharmacodynamics assessment (qPCR)**
- Blood sample for pharmacokinetics and pharmacodynamics assessment
- * Note: for Ethiopia, severe malnutrition will be defined as follows:
 - For patients 4-18 years, MUAC cut-off based on the following MUAC-for-height reference table:

Height	MUAC cut-off for severe malnutrition
65-<110 cm height	< 115 mm
110- <120 cm	< 120 mm
120-<130 cm	< 125 mm
130-<140 cm	< 135 mm
140-<150 cm	< 145 mm
150-<160 cm	< 150 mm
160-<170 cm	< 155 mm
≥170 cm	< 160 mm

- For patients >18 years, MUAC < 170 mm

MUAC is the circumference of the left upper arm and is measured at the mid-point between the tips of the shoulder and elbow.

8.3. Assessment of Efficacy

8.3.1 Clinical assessment of VL

The clinical evaluation* will involve measuring temperature (axillary), spleen size, liver size, body weight at screening, on day 1, 3, 7, 14, 21**, 28 and at all follow-up assessments on day 56 and 210. In addition, the following VL symptoms will be

Confidential Page 40 of 68

^{**} Note: microscopy is mandatory. Culture and qPCR material to be collected if there is remaining material after preparing the slides.

systematically checked at each study visit: fever, abdominal swelling, loss of appetite, diarrhea, coughing, epistaxis or other bleeding signs, jaundice.

The size of the liver will be measured in the midclavicular line for its total span; the spleen size will be measured from the left costal margin on the anterior axillary line to the tip of the spleen medially.

- * Note: for Ethiopia, clinical evaluation will include measurement of MUAC at screening and on day 28, 56 and 210.
- ** Note: D21 visit was only applicable to the subset of patients allocated to PK sampling in arm 2 (now discontinued).

8.3.2. Parasitological assessment

Parasitological assessment will be done at baseline and at day 28 through spleen or bone marrow aspirate and microscopic examination.

Spleen aspirate should not be performed if platelets count is $< 40,000/\text{mm}^3$, Hb $\le 5g/dL$, if the patient has signs of bleeding, jaundice, or if the spleen is not palpable. In these cases, bone marrow aspiration is recommended.

In addition, sites performing splenic aspiration for parasitology must also perform prothrombin time as an additional compulsory screening test to determine whether it is safe to proceed with splenic aspiration. If there is more than a 5 second difference between the normal control value and prothrombin time result obtained, the patient is not eligible for splenic aspiration at that point in time. In this case, the investigator should, either,

a. Administer Vitamin K for 3 days and repeat the prothrombin time test on day 4. If prothrombin time result is within acceptable range (not more than 5 seconds difference from normal control), and all other parameters for splenic aspiration are within the required range, then a splenic aspirate can be done

OR

b. Perform bone marrow aspiration instead

If the site does not have the capability to perform the prothrombin time test, splenic aspiration should not be performed, and bone marrow aspiration should be performed instead.

Due to the risk of hemorrhage post spleen aspiration, the patient must remain under observation. Record pulse and blood pressure every half hour for 4 h, then every hour for 6 h. Patient must remain in bed for 12 hours.

Patient monitoring post-splenic aspiration should strictly be observed as per the study protocol and in-country national VL treatment guidelines. Any suspicion of bleeding such as a drop in blood pressure, rising heart rate, abdominal discomfort or pain, or any other sign as per investigator's judgement should be followed by immediate emergency response measures as per national VL treatment guidelines.

Confidential Page 41 of 68

During the follow-up visits at day 56, day 210 or unscheduled visit, parasitology will be performed when clinically indicated, *i.e.* anytime if suspect of relapse (reappearance of symptoms and signs of VL).

Aspirates will be smeared on slides, stained and read under microscope.

For spleen aspirate, slide reading will be graded as positive or negative according to the standard logarithmic criteria as defined in Table 3.

Table 3 - Standard logarithmic criteria for Visceral Leishmaniasis parasitological diagnosis

Count Oil Immersion x 100			
6+	> 100 parasites per field		
5+	10-100 parasites per field		
4+	1-10 parasites per field		
3+	1-10 parasites per 10 fields		
2+	1-10 parasites per 100 fields		
1+	1-10 parasites per 1000 fields		
0	0 parasite per 1000 fields		

Optionally, if there is sufficient tissue aspirate sample remaining after the slide has been prepared, this will be processed and used for pharmacodynamics analysis (see section 8.4.2.) and culture.

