10.2. Definition of study populations included in the analysis

The following patient populations will be defined for analysis:

- Intention-To-Treat (ITT): all randomized patients in the arms to which they were randomly assigned regardless of their adherence with the inclusion-exclusion criteria, the treatment they received, and subsequent withdrawal from treatment or deviation from the protocol.
- Modified Intention-To-Treat (mITT) or Full Analysis Set (FAS): All randomized
 patients receiving at least one dose of treatment. In case of error of treatment
 allocation, the actual treatment received will be used in the analysis. Modified ITT
 set of patients will be used in the primary efficacy analysis and in safety analysis.
- Set of completers: subset of patients belonging to the FAS, who attend the 6-months follow-up visit. This set will be used in a sensitivity analysis of the primary efficacy analysis. This analysis will be based on the definitive cures.
- Per protocol (PP) set of patients: subset of patients belonging to the FAS and who
 are free from major protocol violations. Major protocol violations are any violation
 which might bias the result of the non-inferiority test. Major violations will be defined
 a priori in the statistical analysis plan. They will be identified and documented
 during the blind review of data. This set of patients will be used in the primary
 sensitivity analysis.

The primary population for efficacy analysis at D210 will be the modified intention to treat population (mITT or FAS). Furthermore, per-protocol set of patients and the set of completers sensitivity analyses will be performed.

All patients enrolled in the study and who have been administered the first dose of study medication will be included in the safety analysis.

Confidential Page 54 of 68

For the secondary endpoint on PK, all subjects exposed to at least one dose of the medication and who have a PK sample collected will be included in the analysis.

Patients' data randomized in arm 2 (PM 14 days/MF 28 days), which recruitment is now discontinued, will be summarized in a descriptive analysis, but not included in the comparative efficacy analysis.

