10.6. Efficacy Analysis

Primary endpoint:

- Definitive cure or treatment success:
- absence of signs and symptoms of VL at D210,
- o no rescue treatment at any time up to D210 (included).
 - Treatment failure:
- o Patient who requires rescue treatment due to any of the following:
 - Initial failure:
 - occurrence of adverse events that leads to treatment discontinuation
 - relapse at any time;
- o death during treatment period or death during follow-up period that is related to VL
- Lost to follow-up at D56 or before.
 - Unconfirmed status at D210:

Confidential Page 55 of 68

 Patient who did not fail at day 28 (initial cure) and at day 56 (probable cure), did not relapse before D210 (no rescue treatment, no signs and symptoms of VL before day 210) and did not attend day 210 visit.

Definitions:

Initial failure: patient who did not respond to the treatment and required rescue therapy within the 28 days treatment period; or patient who had a positive parasitology (by microscopy) at the D28 assessment.

Relapse: patient who had responded to treatment and had a negative parasitology at the D28 assessment, but who presents signs and/or symptoms of VL during follow-up, with VL confirmed by presence of parasites in a parasitological investigation.

Secondary efficacy endpoints:

Initial cure - cure at the end of treatment (Day 28), defined as recovery of clinical signs and symptoms; absence of parasites (microscopy) and no rescue treatment administered at Day 28 or before.

Probable cure - absence of clinical signs and symptoms of VL at D56 and no prior requirement for rescue treatment.

Primary Efficacy Analysis

The primary efficacy analysis will be based on

- the modified intention to treat population (mITT or FAS);
- the primary endpoint (cure at D210);
- the primary imputation approach (see below) and the primary test of non-inferiority, which is the Blackwelder test.
- primary comparison: MF-PM 14 days vs SSG-PM.

The significance limit will be 0.025 (one-sided). If the non-inferiority test is significant the test of superiority will be performed.

Handling of unconfirmed status

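### The protocol of this open-label trial states no masking of the reader of the slides that can define day 28 failure and are needed to confirm relapse; coding the slides is a cheap improvement

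*Combined protocol and SAP*

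**What the plan says.** Section 7.6: "This is an un-blinded open label study".

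Section 8.3.2 sets the timing: "Parasitological assessment will be done at baseline and at day 28 through spleen or bone marrow aspirate and microscopic examination". After day 28, "parasitology will be performed when clinically indicated". On the reading itself it says: "Aspirates will be smeared on slides, stained and read under microscope". It then adds: "For spleen aspirate, slide reading will be graded as positive or negative according to the standard logarithmic criteria as defined in Table 3". Table 3 separates grade 0 from grade 1+ by whether any parasite is seen in 1000 fields. The section names no reader and mentions no masking, number of readings or adjudication.

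Section 10.6 gives two routes to initial failure. One is clinical: "patient who did not respond to the treatment and required rescue therapy within the 28 days treatment period". The other is the slide: "patient who had a positive parasitology (by microscopy) at the D28 assessment". Relapse requires signs or symptoms in follow-up together with parasitological confirmation. Section 7.8 lists a positive day 28 parasitology, clinical non-response, or both, as grounds for rescue. Section 2.2.1 makes definitive cure depend on the clinical picture at day 210 and on no rescue having been required.

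Culture and tissue qPCR use whatever material is left after the slides are made (sections 8.2 and 8.3.2), and section 10.6 gives them no part in the primary endpoint. The only masking mentioned anywhere is in section 10.2, where major violations are identified "during the blind review of data". That concerns the per-protocol set, not the slides.

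**The concern.** The clinical parts of the endpoint have to be judged by people who know the treatment. The slide does not: it can be read by someone who has not been told the arm. At low parasite density the result depends on how thoroughly the slide is searched. For bone marrow, which section 8.3.2 allows and in some cases requires, no grading criterion is stated at all. A reader who knows the arm could, without intending to, search one arm's slides harder than the other's.

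With few failures expected and a margin of 7 points, a small net difference in reading could matter. Towards MF/PM it would raise the chance of a false claim of non-inferiority; against MF/PM it would cost power.

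**Working it through.** **1. The plan's own figures (section 10.1).** Inputs: cure 93% for MF/PM and 91% for SSG-PM, margin 7 points, one-sided alpha 0.025, power at least 80%, 153 per arm, 10% loss to follow-up.

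- 153/0.90 = 170, as stated.
- Unpooled normal approximation at 153: SE = √[(0.93×0.07 + 0.91×0.09)/153] = 0.0310, and power = Φ(0.09/0.0310 − 1.96) = 82.7%.
- Exact binomial power of the Farrington-Manning score test at 153 is 80.3%.

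Either way 153 gives at least 80%. Masking changes no sample size.

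**2. What a misread slide does to the day 210 endpoint** (sections 2.2.1, 7.8, 10.6).

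| Slide | Misread as negative | Misread as positive |
|---|---|---|
| Day 28 | Patient stays in follow-up and can still relapse or have signs at day 210. The endpoint changes only if the patient remains well and unrescued. | Initial failure and a ground for rescue; not reversed later. |
| Suspected relapse | Relapse not confirmed. If signs are present at day 210, the patient is still not a definitive cure. | Relapse and a ground for rescue; not reversed later. |

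**3. Ceiling per slide.** With 170 per arm analysed, 1/170 = 0.59 points. For false negatives this is a maximum, because later follow-up can restore the failure.

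**4. How many failures could rest on a slide.** Expected failures are 170×0.07 = 11.9 (arm 1) and 170×0.09 = 15.3 (arm 3). These cover every cause in section 10.6, including adverse events leading to rescue, VL-related death and loss to follow-up by day 56.

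The only split by time for one cohort is in section 1: 30 children on miltefosine monotherapy, 96.7% cured at day 28 and 90.0% at 6 months, that is 1 and 3 failures. If one third also applied here (an assumption resting on 3 failures under a different regimen), about 4 of arm 1's 12 would appear by day 28, by any route. False positives have no such cap: about 0.91×170 = 155 patients in arm 3 are expected to be cured.

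**5. Illustration.** The documents give no reader error rate, so the net shift b is an assumption, applied to arm 1's observed cure rate. Unpooled normal approximation, 153 per arm:

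- Type I error at the margin (true rates 84% and 91%), shift favouring arm 1: Φ(b/SE − 1.96), with SE = √[((0.84+b)(0.16−b) + 0.91×0.09)/153].
- Power at 93% and 91%, shift against arm 1: Φ((0.09−b)/SE − 1.96), with SE = √[((0.93−b)(0.07+b) + 0.91×0.09)/153].

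| Net shift b | Patients of 153 | Type I error, shift favours arm 1 | Power, shift against arm 1 |
|---|---|---|---|
| 0 | 0 | 2.5% | 82.7% |
| 1 point | 1.5 | 4.6% | 70.9% |
| 2 points | 3.1 | 7.9% | 57.1% |
| 3 points | 4.6 | 13.1% | 43.3% |

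Exact binomial type I error for the same test is 2.7%, 4.9%, 8.4% and 13.7%.

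The lower rows need a lot from missed day 28 positives alone. At the margin arm 1 has 0.16×153 = 24.5 failures. One third of these is 8.2, so 4.6 lasting misses would be more than half of all day 28 failures.

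**The case against.** Much of the case on the other side stands.

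- **Follow-up corrects missed positives.** The endpoint is cure at day 210, so a missed day 28 positive often fails later anyway. This stands, and makes 0.59 points a ceiling. It does not help with false positives.
- **Slides are not the only route.** A reader might infer that the slide settles both initial failure and relapse. The documents do not support this: initial failure and day 28 rescue each have a clinical route, and relapse first needs signs or symptoms.
- **Number of readings.** A reader might infer that each slide is read only once. Section 8.3.2 is silent, and silence does not establish it.
- **Direction.** Because the protocol is open about the advantages it expects of MF/PM, a reader might infer a bias towards non-inferiority. Nothing in the documents shows this; a sceptical reader could search arm 1 slides harder.
- **The count is fixed.** For spleen slides Table 3 already sets 1000 fields. That limits discretion but does not conceal the arm, and it is not stated for bone marrow.
- **A laboratory SOP may cover this.** It may, and patient numbers are sequential with nothing to suggest that they encode the arm (section 6). But the protocol cites no such rule.
- **Section 10.2.** A reader might take the blind data review there as part of the same problem. It is a separate matter: it serves the per-protocol sensitivity analysis and has no bearing on how slides are read.

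**Conclusion.** The gap is real and modest. The trial is open label, no masking of the slide reader is stated, and the slide is the only named laboratory criterion feeding the primary endpoint. Differential reading could bias the comparison either way.

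Its size cannot be derived from the documents. What can be said is that one misread slide is worth at most 0.59 points, that only a subset of the expected failures depends on a slide, and that a net shift of 1 to 2 points (about 2 to 3 patients of 153) would move type I error at the margin from 2.5% to about 5% to 8%, or power from 82.7% to about 71% to 57%. Those shifts are assumptions, not estimates.

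This is a cheap improvement to conduct. It is not evidence that the result would be biased, and it calls for no change to the sample size or the primary analysis.

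**What to change.** Add to section 8.3.2: day 28 and suspected-relapse slides carry only a study or accession number; the existing laboratory reader is not told the treatment arm; the grade is recorded and signed before it is released to the clinician. If a laboratory SOP already requires this, cite it there.

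The cost is a labelling rule and a line in the SOP. Laboratory technicians are already on the study team (section 12.2), allocation is obtained by the investigator online or by phone (section 6), and day 28 is an outpatient visit in every arm (section 8.1), so nothing described requires the reader to know the arm.

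There are two limits. Masking may be imperfect at small sites: at day 28 a miltefosine PK sample is taken only in the MF/PM arms and an ECG only in the SSG-PM arm (section 5, footnotes), so a technician who also handles the blood tubes could infer the allocation. And the rule covers the reading only: unmasked clinicians still decide whom to aspirate in follow-up and whom to rescue, so bias is reduced, not eliminated.
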